A major barrier to adherence is lack of knowledge about how to follow a SRD. Most educational interventions have focused on improving knowledge by teaching patients specific skills including how to read food labels, how to choose low sodium foods when eating out, and how to modify their usual diet. The majority of these educational self-management interventions have focused only on patients. Family members are an overlooked but essential resource for support of patient self-management. Their lack of knowledge or support in following the SRD can be an important barrier to adherence. Their perceived difficulty in managing a separate diet for the patient with HF contributes to feelings of burden. However, the same level of sodium recommended for patients with HF is now recommended for all healthy adults to prevent chronic disease, making a whole family intervention for restricting sodium in the diet an ideal approach.

Other important barriers to adherence to the SRD are the perceived poor taste of low sodium foods and an appetite for high sodium foods that make dietary changes difficult. As people age, their perception of saltiness is diminished, causing an increased preference for high salt (sodium) foods. Complex physiologic and evolutionary mechanisms operate to maintain preference for foods high in sodium. Abrupt and marked reductions in sodium intake can lead to sodium-seeking behaviors; thus changing dietary preferences requires at least 8 weeks to reach a new hedonic state and to reset sodium taste buds. Thus, an intervention that uses a gradual adaptation strategy should produce the best long-term adherence results.

**Objectives:** List your research objectives. You may reference grant application/sponsor's relevant protocol pages and attach as an appendix in the E-IRB "Additional Information" section, however, a summary paragraph must be provided in the text box below.

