The long-term objective of this program of research is to improve outcomes of patients with heart failure (HF) by increasing their adherence to a sodium restricted diet (SRD). The purpose of the proposed randomized, controlled trial is to test the effects of the Family Sodium Watcher Program (Family SWaP), designed to improve both patients' and caregivers' adherence to a SRD. The Family SWaP program is an innovative self-management intervention using a gradual adaptation strategy and an electronic salt monitoring device that allows individuals to monitor and over time reduce sodium content in their food. Given the recommendation that all individuals should consume a SRD, the intervention has the potential for expanded application beyond patients who need to follow a SRD for cardiovascular reasons to everyone consuming a diet high in sodium.

**Study Design:** Describe the study design (e.g., single/double blind, parallel, crossover, etc.). Indicate whether or not the subjects will receive placebo medication at some point in the research procedures. Also, indicate whether or not the subjects will be randomized in this study. You may reference sponsor's protocol pages and attach as an appendix in the E-IRB "Additional Information" section, however, a summary paragraph must be provided in the text box below. (Including the study design table from a sponsor's protocol is helpful to IRB members.)

**Community-Based Participatory Research:** If you are conducting [community-based participatory research \(CBPR\)](#), describe strategies for involvement of community members in the design and implementation of the study, and dissemination of results from the study.

**Research Repositories:** If the purpose of this submission is to establish a Research Repository (bank, registry) indicate whether the material you plan to collect would or would not be available from a commercial supplier, clinical lab, or established IRB approved research repository. Provide scientific justification for establishment of an additional repository collecting duplicate material. Describe the repository design and operating procedures. For relevant information to include, see the UK Research Biospecimen Bank Guidance [\[PDF\]](#) or the UK Research Registry Guidance [\[PDF\]](#)

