A two-group, randomized controlled design will be used to determine the effect of Family SWaP on sodium intake of patients with HF and family caregivers (Figure 1). Dyads will be randomly assigned to intervention or usual care group using a stratified randomization strategy after we determine patients' adherence level to SRD at baseline. Because adherence level at the baseline may affect outcomes, stratification is needed to insure similar sample characteristics between Family SWaP and usual care groups. Non-adherence will be defined as a 24-hour urinary sodium excretion greater than 3000 mg. The 3000 mg 24-hour urinary sodium excretion cut point was chosen because it is the upper limit of sodium intake recommended for patients with HF. The intervention will be delivered to both adherent and non-adherent patients because it has not known whether the intervention delivered to a dyad can maximize their adherence behavior or promote long-term adherence behavior. The intervention will be delivered 16 weeks (6 weekly 45 minutes sessions and 5 bi-weekly 20 minutes sessions).using video conferencing technology via digital device (i.e., ipad). Post-intervention effects will be assessed at 4 and 12 months to identify short- term and long-term post-intervention. We will collect hospitalization information up to 12 months by phone follow up. Dependent variables include adherence to the SRD, symptom distress, knowledge of SRD, perceived control, perceived social support, quality of life, and caregiving burden (caregiver only), symptom distress (patient only), and rehospitalization (patient only). We will also collect 4 variables to evaluate salt taste: salt food preference, sensory density, and diet quality. Qualitative data regarding salt taste preference and family experiences.

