A total of 300 patient-caregiver dyads (i.e., 600 individuals; see sample size justification in data analysis section) will be randomized into intervention and usual care groups. Eligible patients will have (1) have a diagnosis of chronic heart failure with either preserved or non- preserved ejection fraction (2) be able to speak and write English, (3) have a phone in home and (4) without cognitive impairment of dementia and Alzheimer. Patients will be excluded if they have a co- existing terminal illness, or have a dietary prescription at odds with following a 2-3 gram sodium diet (e.g., clinician does not support use of a SRD). Patients without dedicated caregivers are excluded in this study. Improving outcomes of patients without caregivers are important to study, but it is not appropriate to include them in this study. After this study demonstrate effect of gradual adaptation strategy, it will be important to test the effect on patients without caregivers by providing support from nurses. A family member is eligible if he/she is: (1) a primary caregiver identified by a patient; (2) the spouse, committed partner, or family member living with the HF patient; (3) able to speak and understand English; (4) without cognitive impairment of dementia and Alzheimer. Despite the fact that HF is equally distributed between the genders, the representation of women in many studies of HF has been low. We plan to enroll 50% female patients. The population of HF patients at the University of Kentucky Medical Center (UKMC) is sufficient and approximately 50% are women, so we do not anticipate difficulty in obtaining an adequate sample of women and men with HF for this study. Based on our dyadic study, we expected at least 10% more female caregivers than male caregivers. This is consistent with the common observation that more females take on the caregiver role than males. Based on national estimates and University of Kentucky Chandler Hospital (UKCH) discharge data, planned enrollment in this study is 80% Caucasian and 20% African American.

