#### Mailing recruitment letters on behalf of the Investigator

The Center for Clinical and Translational Science (CCTS) Participant Recruitment Core manages the Investigator/Researcher approval process for drafting recruitment letters from the primary physician for initial contact of eligible patients generated from the EDT.

**Potential Risks:** Describe any potential risks or likely adverse effects of the drugs, biologics, devices or procedures subjects may encounter while in the study. Please describe any physical, psychological, social, legal or other risks and assess their likelihood and seriousness.

Protection against breach of confidentiality is provided by training all individuals involved in the research process about the necessity for complete confidentiality, housing all data collected in locked file cabinets in an access-restricted area, and by use of password protected computers and secure servers. Genetic data will be accessible only to study personnel. Potential risks of the study are related to questionnaire administration. Participants may experience some anxiety or psychological distress when completing questionnaires. In our experience, less than 3% of patients report this effect and when they do it is relatively transient. The acquisition of urine specimen poses no known risks. There is a slight risk for emotional upset as the qualitative questions will focus on family

dynamics and differences regarding low sodium diet.

[Back to Top](#)

**Safety Precautions:** Describe the procedures for protecting against or minimizing any potential risks, *including risks of breach of confidentiality or invasion of privacy*. Where appropriate, discuss provisions for ensuring necessary medical or professional intervention in the event of adverse events, or unanticipated problems involving subjects. Also, where appropriate, describe the provisions for monitoring the data collected to ensure the safety of subjects. If vulnerable populations other than adults with impaired consent capacity are to be recruited, describe additional safeguards for protecting the subjects' rights and welfare.

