- a. Periodic Review: The Principle Investigator (PI) will hold weekly staff meetings for the first month of enrollment then bi-weekly thereafter. The staff meeting will include the PI, co- investigators, project director, nurses in charge of recruitment and the intervention, and the data manager. The meeting will include evaluation of all research procedures, fidelity to protocol, discussion of newly enrolled participants, and review of status of all formally enrolled participants including all adverse events. Adverse events will be reviewed to determine if changes in the protocol are indicated. Participant demographics to date, recruitment progress, and difficulties encountered during enrollment, an update on data entry, and any other issues or concerns that have arisen since the last research team meeting will also be discussed.
- b. Adverse Events: The educational intervention study is minimal risk. We do not anticipate moderate, severe, life-threatening or fatal AEs. Regardless, adverse events will be defined in accordance with Federal Regulation 21CFR §56.108(b)(1) and 45 CFR 46.103(b)(5). Adverse events that are unexpected and related to the study will be promptly reported to the University Institutional Review Board (IRB). The Data and Safety Monitoring Plan for the proposed project incorporates the policies on human subject data and safety monitoring specified by the University of Kentucky IRB.
- c. Plan for Safety Review: A methodical review of all procedures will be an integral part of each research team meeting. Review will include discussion of protocol to ensure adherence, discussion of procedures to insure confidentiality is maintained and that data are collected with minimal risk for violations of confidentiality. A meeting involving the PI, co- investigators, and research nurses will be called if an unexpected adverse event occurs.
- d. Plan for Data Quality: The research design, methods and procedures will be reviewed by all members of the research team during staff meetings. Meetings with PI and data manager will be conducted every 3 months to verify accuracy of data entry, identify missing data, and run preliminary analyses of demographic, to verify enrollment targets, and outcomes. Data entry errors will be corrected and plans will be developed to address any systematic problems related to data entry and integrity.

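### The risk section omits the coached sodium reduction, and no stated method elicits non-hospitalized adverse events alike in both arms or in caregivers

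*Combined protocol and SAP*

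**What the plan says.** **Risk statement.** Potential Risks states "Potential risks of the study are related to questionnaire administration". The same text addresses confidentiality, says urine collection carries no known risk, and mentions possible upset from the qualitative questions. The intervention does not appear.

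**Intervention.** Objectives describes a gradual programme with an "electronic salt monitoring device that allows individuals to monitor and over time reduce sodium content in their food". Study Design gives 6 weekly and 5 bi-weekly sessions over 16 weeks and adds: "The intervention will be delivered to both adherent and non-adherent patients". Caregivers take part as members of the dyad.

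**Safety plan.** Data and Safety Monitoring, item b, states "We do not anticipate moderate, severe, life-threatening or fatal AEs". Events that are both unexpected and study-related go promptly to the IRB. Item a has staff meetings review all adverse events and decide from them whether the protocol should change. Neither item gives a question, checklist or schedule for finding these events.

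**What is collected.** Under Research Procedures, both arms follow the same data collection. Monthly calls and a logbook record hospitalizations for 12 months, a nurse blinded to group confirms them, and questionnaires are repeated at both follow-ups. Study Design lists symptom distress once without restriction and once as patient only; the symptom form among the Data Collection attachments is a patient form. Rehospitalization is patient only. In the SAP, Specific Aim 2 compares time to rehospitalization or death by arm. The SAP has no adverse event summary.

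**The concern.** The plan treats the diet as active when it describes benefit (Benefit vs. Risk expects better symptoms and outcomes from adherence) but does not mention it under risk. Study Population nevertheless excludes patients who "have a dietary prescription at odds with following a 2-3 gram sodium diet", so the plan does not regard the diet as suitable for everyone.

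The statistical issue is ascertainment. If an event short of hospital admission comes to light only when someone mentions it, the count depends on how often people are spoken to, and the arms differ in that by design. Staff meetings that include the intervention nurses would then weigh protocol changes on counts that partly reflect contact frequency. Events that nobody raises would go unrecorded in either arm. This cannot be repaired at analysis, because the answers would never have been collected.

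**Working it through.** The documents give no adverse event rate or expected count, so there is no figure of the plan's own to reproduce. The check has two parts: which harm-related information is solicited, and how unequal the contacts are.

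**1. What is solicited**

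- Hospitalization: monthly, both arms, blinded confirmation, patients only.
- Symptom distress: at assessments, both arms, on a patient form. Whether the 4-month assessment is counted from the end of the programme (Research Procedures) or from baseline, no assessment falls between baseline and the end of the 16 weeks of coaching.
- Depression: Safety Precautions describes a PHQ-9 screen with referral for patients.
- Other events between assessments, and adverse events in caregivers: no method stated.

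**2. Contacts**

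Inputs: 6 weekly sessions of 45 minutes and 5 bi-weekly sessions of 20 minutes (Study Design); monthly calls for 12 months in both arms (Research Procedures). Assumptions: 12 calls in the year, about 4 of them during the 16 weeks, and no study sessions in usual care.

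- Length: 6 × 1 + 5 × 2 = 16 weeks, matching the plan.
- Extra sessions: 6 + 5 = 11, or 6 × 45 + 5 × 20 = 370 minutes.
- Over 12 months: 12 + 11 = 23 v 12, ratio 1.92. Adding three assessments to each arm: 26 v 15, ratio 1.73.
- During the 16 weeks: 4 + 11 = 15 v 4, ratio 3.75.

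**3. Effect on spontaneous reports when the arms do not truly differ**

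Let q be the chance that a participant volunteers an event at any one contact, equal in both arms. The share with at least one report after k contacts is 1 − (1 − q)^k. The documents give no q, so a range is shown.

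| q (assumed) | 12 months, 23 v 12 contacts | 16 weeks, 15 v 4 contacts |
|---|---|---|
| 0.01 | 20.6% v 11.4% | 14.0% v 3.9% |
| 0.02 | 37.2% v 21.5% | 26.1% v 7.8% |
| 0.05 | 69.3% v 46.0% | 53.7% v 18.5% |
| 0.10 | 91.1% v 71.8% | 79.4% v 34.4% |

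For scale, assume 1:1 allocation of the 300 dyads (the ratio is not stated), so 150 per arm. At q = 0.01 over 12 months this gives 150 × 0.206 ≈ 31 patients v 150 × 0.114 ≈ 17. A two-sided 5% test would call such a spurious difference significant with probability 0.59 at q = 0.01, rising to 0.99 at q = 0.10. The SAP plans no such test; the figure only shows that the artefact need not be small.

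**The case against.** The best defence is that the plan already collects a good deal on harm, symmetrically. This largely stands. A reader might infer that hospitalizations are the only events asked about, but symptom distress is an outcome repeated in both arms. Subject Recruitment Methods & Privacy also mentions a study form for hospitalization, event and survival data. The forms were not supplied, so they may contain relevant items.

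A reader might also infer that prompt reporting is weakened because the diet is missing from the risk list. The text does not support that. Item b defines adverse events by federal regulation and does not refer to Potential Risks; if anything, an unlisted event counts more easily as unexpected.

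Nor does the Background show that the diet injures patients. Its statement that "Abrupt and marked reductions in sodium intake can lead to sodium-seeking behaviors" concerns preference and adherence, and is the reason for a gradual approach. The same section says the recommended sodium level for these patients now applies to healthy adults too. The exclusion for conflicting prescriptions is a safeguard.

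Finally, that other events arrive unsolicited is inferred from silence, and the contact imbalance depends on what the control group receives. Research Procedures describes standard care only, while Available Alternative Treatment(s) once labels the control an attention group. These points limit the claim. They do not supply a stated method for eliciting non-hospitalized events on a common schedule, or any in caregivers.

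**Conclusion.** The concern holds in a limited form. The sodium reduction is absent from the risk text. Outside hospitalization and patient symptom distress, the supplied text states no equal-schedule elicitation of adverse events in the two arms and none for caregivers, although adverse event review may change the protocol.

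With 11 extra sessions, the intervention arm has about 1.9 times the contacts over 12 months and 3.75 times during coaching, so spontaneous reports would tend to count against the intervention. This rests on 12 monthly calls, no attention contacts in usual care, and events being recorded mainly when volunteered. The percentages depend on an assumed q.

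It would go too far to conclude that the trial can say nothing fair about harm. Rehospitalization is solicited monthly and confirmed by a blinded nurse, rehospitalization or death is compared by arm, and symptom distress is measured in both arms. The gap is non-hospitalized events between assessments and adverse events in caregivers. Closing it is a cheap improvement worth making.

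**What to change.** 1. In Potential Risks, name the sodium reduction as a possible source of study risk, for patients and caregivers.
2. In the monthly calls already planned for both arms, ask patients and caregivers the same fixed adverse event questions, worded identically by arm. The investigators should choose the content, after checking what the attached forms already ask.
3. Add to the SAP a by-arm summary of these solicited answers, separately for patients and caregivers. List events volunteered in intervention sessions separately and keep them out of the comparison.
4. Reconcile Research Procedures with Available Alternative Treatment(s) on whether the control group receives attention contacts.

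The cost is slightly longer calls, one extra table and a short edit to the risk text. Diet targets, eligibility and care are unchanged.

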## **Statistical Analysis Plan**

**Specific Aim 1:** Repeated measures analysis of variance (ANOVA) will be used to assess differences between intervention and control groups on outcomes variables over time. Post-hoc analysis will be based on Fisher's least significant difference procedure for pairwise comparisons. Baseline comparisons between those who dropped out and those who completed all three waves of data collection will be determined using two-sample t-tests or chi-square tests, and the rate of retention will be compared between the two treatment arms using the chi-square test of association to assess whether differential drop-out occurred.

**Specific Aim 2:** Kaplan-Myer survival analysis with a logrank test will be used to make an overall comparison between time to rehospitalization or death event between intervention and control groups. Cox proportional hazards model will be used to estimate the hazard ratio of intervention effect on the prediction of the end-point of rehospitalization or death compared to usual care group, while controlling potential compounding factors.

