We will also gather hospitalization/event/survival data using a form we designed for this purpose. We will have the nurse recruiters/liaisons at St. Claire and Baptist Health Lexington hospital systems gather this data, complete our form and send it to us using secure email.

The CCTS EDT will provide a list of patients that meet the enclosed inclusion/exclusion criteria; as well as, basic demographics (full name, medical record number, sex, race, date of birth) and attending/primary physician name and service.

The attending/primary physician will be contacted by the Investigator study coordinator to approach the patient to obtain permission for the PI/study coordinator to contact them. No cold calls/ contact will be made directly with the patient without obtaining permission through their attending physician. A card will be supplied to the patient from the attending/primary physician so the patient can complete contact information for the Investigator. Once permission has been granted by the patient, the Investigator study coordinator will contact the patient for recruitment into the study.

The CCTS EDT will provide a list of patients that meet the enclosed inclusion/exclusion criteria; as well as, basic demographics (full name, medical record number, sex, race, date of birth) and attending/primary physician name and service to the CCTS Participant Recruitment Coordinator.

The attending/primary physician will be contacted by the Participant Recruitment Coordinator to approach the patient to obtain permission for the PI/study coordinator to contact them. A draft letter regarding the study recruitment will be supplied to the attending/primary physician for approval prior to mailing to patients. No cold calls/ contact will be made directly with the patient without obtaining permission through their attending/primary physician. Once permission has been granted by the attending/primary physician, the CCTS Participant Recruitment Coordinator will contact the patient for recruitment into the study via mailings.

[Back to Top](#)

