After eligible patient-caregiver dyads sign the consent forms, they will participant in this study. Baseline data will be collected during a home visit. At the baseline assessment, they will fill out questionnaires using the RedCap system and collect 24-hour urine specimens. Urine containers, collection devices (urinals for men and toilet "hats" for women) and written instructions will be provided. The research assistant will interview participants to obtain demographic characteristics and to confirm their comorbidities. Information about demographics and comorbidities will be obtained using a structured questionnaire in interview. A research assistant and the dyads will set up the starting day of urine collection within 3 days of completion of questionnaires and pick up dyad's urine specimens in the dyad's home and deliver University of Kentucky Chandler Hospital Laboratory to determine 24-hour urinary sodium excretion level. Additional data collection for qualitative data, and diet quality will be also collected by home visiting. The medical chart will be reviewed to confirm only patients' comorbidities. After patients are categorized as adherent or non- adherent using 3000mg urine sodium cut point, the dyads will be randomly assigned to the Family SWaP intervention or usual care group using stratified randomization. Caregivers' adherence level at baseline will not be used in randomization but will be used to compare adherence at follow up. Dyads in the Family SWaP intervention will participate in a 16-week intervention delivered by the interventionist. The usual care patients will receive the standard medical and nursing care for HF patients provided at the clinics from which they were recruited. The usual care dyads will participate in the same data collection procedures as dyads in the intervention group. Follow-up data collection will be conducted 4 and 12 months after the intervention group completes the 16 week intervention to evaluate short and long term effects. At each follow-up, patient-caregiver dyads will complete the same questionnaires as baseline. Self-report of all hospitalization events will be collected from patients/family caregiver via monthly phone calls and a hospitalization logbook kept by the dyad for 12months. The medical record and administrative database will be queried to confirm rehospitalizations by the research nurse who will be blinded to the study group assignment. Data from the optional recorded interviews will be transcribed by a HIPAA compliant third party transcription service (REV).

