There is no monetary incentive to compensate for their time during 12 months. However, each dyad (patients and their family caregiver dyad) who participant in this study will receive an iPad per family at the beginning of the study. If any one of the dyad members withdraws the study before three assessments complete, we consider patient-caregiver dyad as a unit of the study will end the study and they should return the iPad that will be given during the study. When two dyad members complete all three assessments during 12 months study, the dyad will keep the iPad. Free data plan will be provided for only dyads that don't have home Wi-Fi access during the study (12 months).

**Costs to Subjects:** Describe any costs for care associated with research (including a breakdown of standard of care procedures versus research procedures), costs of test drugs or devices, and research procedure costs that are the subject's responsibility as a consequence of participating in the research. Describe any offer for reimbursement of costs by the sponsor for research related injury care.

There will be no additional costs to the participants and no personal travel costs to the research site.

**Data and Safety Monitoring:** The IRB requires review and approval of data and safety monitoring plans for greater than minimal risk research, clinical research, or NIH-funded/FDA-regulated clinical investigations.

If you are conducting greater than minimal risk research, clinical research, or your clinical investigation is NIH-funded/FDA-regulated, describe your Data and Safety Monitoring Plan (DSMP). [Click here for additional guidance on developing a Data and Safety Monitoring Plan.](#)

If this is a *non-sponsored investigator-initiated* protocol considered greater than minimal risk research, clinical research, or your clinical investigation is FDA-regulated, *and* if you are planning on using a Data and Safety Monitoring Board (DSMB) as part of your

DSMP, [click here for additional guidance](#) for information to include with your IRB application.

If relying on an independent agent or committee for DSMB services, it is the PI's responsibility to establish the services with the agent or committee. Please be reminded that the PI must submit DSMB reports to the IRB via modification or continuing review. 

We have developed a detailed Data Safety Monitoring Plan that includes the following elements.

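### The dyad withdrawal rule has no exception for the patient's Aim 2 event follow-up, so a caregiver-only exit can lose rehospitalizations and deaths that records could supply, and the survival analysis has no rule for such exits

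*Combined protocol and SAP*

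**What the plan says.** The withdrawal rule is in the Payment section of the Research Description. Its trigger is "If any one of the dyad members withdraws the study before three assessments complete". Its consequence is "we consider patient-caregiver dyad as a unit of the study will end the study", and the iPad must also be returned. No section makes an exception for the patient's event follow-up.

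For Specific Aim 2 the SAP states: "Kaplan-Myer survival analysis with a logrank test will be used to make an overall comparison between time to rehospitalization or death event". It adds that a "Cox proportional hazards model will be used to estimate the hazard ratio of intervention effect", adjusted for factors that it does not name. It gives no censoring rule, no handling of dyad withdrawal and no sensitivity analysis. Its drop-out checks are under Specific Aim 1: a baseline comparison of drop-outs with completers, and "the rate of retention will be compared between the two treatment arms using the chi-square test of association".

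The Study Design section lists rehospitalization as an outcome of patients only. Events reach the study by three routes:

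- Research Procedures: self-report "via monthly phone calls and a hospitalization logbook kept by the dyad for 12months".
- Research Procedures: "The medical record and administrative database will be queried to confirm rehospitalizations", by a nurse blinded to group.
- Subject Recruitment Methods & Privacy: "We will also gather hospitalization/event/survival data using a form we designed for this purpose", completed by staff at two partner hospital systems.

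**The concern.** Read as written, the Payment rule lets a caregiver's decision remove a patient who may be willing to stay and who alone carries the Aim 2 endpoint. The calls and logbook need a participating dyad. The record query and the hospital forms do not, so the loss of events is avoidable.

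The survival methods would treat an exit as independent censoring (for Cox, independent given the covariates). That may fail if caregivers tend to leave when the patient worsens. The documents do not say why caregivers leave. They do list caregiving burden as an outcome, and the Background links burden to managing a separate diet.

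Two things are at stake. Lost events lower power. If the link between decline and exit differs by arm, the hazard ratio and its test are also biased, in a direction that the retained data cannot show.

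**Working it through.** **No figure to reproduce.** The documents give no event rate, hazard ratio, power or withdrawal rate for Aim 2. The 300 dyads come without their derivation in the text available. Every rate below is therefore an assumption, with 150 patients per arm (1:1 assumed) and 12 months of follow-up.

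**Check 1: exit tracks patient frailty** (1,500 simulated trials per setting, unadjusted Cox).

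The event hazard is a baseline rate × gamma frailty × HR in the intervention arm, calibrated to a 40% usual-care 12-month risk. Frailty variance is 0.5 or 1.0. The withdrawal hazard is constant or proportional to frailty, by arm, calibrated so that 10% or 20% of dyads leave event-free. With no effect, expected events are 300 × 0.40 = 120.

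- Events lost by stopping at exit: about 7 to 24 of 120, or 7/120 = 6% to 24/120 = 20%.
- True HR 1.00, exit tracking frailty in the intervention arm only: estimated HR 0.97 to 0.90. In the usual-care arm only: 1.02 to 1.13.
- Two-sided type I error: 4.6-6.4% at 10% exit, about 6% at 20% exit with variance 0.5, and about 8-9% only at 20% exit with variance 1.
- True conditional HR 0.70, variance 1, 20% exit: complete follow-up gives about 0.75. Stopping at exit gives about 0.67 or 0.83, depending on the arm.
- Exit tracking frailty equally in both arms: no bias in the HR. Power at HR 0.70 (variance 1, 20% exit) falls from about 34% to 27%.

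**Check 2: exit shortly after decline** (2,000 simulated trials per setting).

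Event hazard is 0.02 per month, decline onset 0.04 per month, the event hazard is 8-fold after decline, and background withdrawal is 0.005 per month. The chance that the dyad leaves just after decline varies by arm. With no effect, complete follow-up gives 113 events, a Kaplan-Meier 12-month risk of about 0.377, HR 1.00 and about 5% rejection. Stopping at exit gives:

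| Exit after decline, usual care / intervention | Events | 12-month risk, usual care / intervention | HR | Rejection |
|---|---|---|---|---|
| 25% / 25% | 95 | 0.346 / 0.345 | 1.00 | 6.2% |
| 50% / 50% | 81 | 0.309 / 0.310 | 1.00 | 5.0% |
| 15% / 35% | 95 | 0.359 / 0.333 | 0.92 | 7.1% |
| 20% / 50% | 89 | 0.352 / 0.309 | 0.86 | 11.5% |
| 35% / 15% | 95 | 0.332 / 0.358 | 1.09 | 7.3% |

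In the first two rows the loss is (113 − 95)/113 = 16% and (113 − 81)/113 = 28% of events. The hazard ratio holds, but absolute risk is understated in both arms. With an assumed HR of 0.70 before decline, complete follow-up gives 0.71, and the last three rows become 0.64, 0.60 and 0.78.

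**How much can be recovered.** Both checks treat every exit as recoverable. Some patients will leave on their own account and refuse record access. If half of exits are of that kind (an assumption), the worst HR below 1 in check 1 moves from 0.90 to about 0.95 after the fix, not to 1.00.

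**The case against.** A reader might infer that the protocol orders event collection to stop when a caregiver leaves. It does not say so. The rule is one loosely worded sentence in answer to a question about payment, and the sections on records and hospital forms contain no such stop. Consent pages, where withdrawal terms might appear, are not available. This stands as a limit on certainty. However, the sentence gives two consequences, ending the study and returning the iPad, and no other text limits the first. If only the second was meant, one sentence settles it.

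A reader might also infer that the heavier schedule in the intervention arm (6 × 45 + 5 × 20 = 370 minutes) makes its exits informative. It does not by itself. Exits caused by session load alone are unrelated to the patient's risk and do not bias the hazard ratio. The planned retention test would show a difference in exit rates, but not a link to decline.

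The planned Cox model is adjusted and the simulated one was not, so covariates might remove some of the bias. How much cannot be judged, because they are not named.

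Finally, patients who leave lose the monthly calls, and the record query is worded as confirming reported events. Keeping them at risk with weaker detection could introduce a bias of its own. This objection is sound, and the fix has to deal with it.

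**Conclusion.** The concern holds as an avoidable loss of events and a missing analysis rule. It does not show that the Aim 2 result would be biased. Under the frailty assumptions, 6-20% of events are lost and a true HR of 1.00 is estimated at about 0.90 to 1.13 when exit tracks frailty in one arm only. Type I error is then near 5-6% in most settings and about 8-9% only in the extreme one. The sharper decline mechanism, with unequal exit by arm, gives 0.86 to 1.09 and 7-12%. With equal tracking the hazard ratio is essentially unbiased, leaving lower power and, under the decline mechanism, understated absolute risk.

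Three limits apply: all rates are assumed, no document links exit to decline, and only exits where the patient still permits record access are recoverable. The change is worth making because it is cheap, and it may be hard to make later if permission for record review after exit was never obtained.

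**What to change.** **Protocol (Payment and Research Procedures).** State that withdrawal of one member ends the programme, the assessments and iPad use. State that it does not end the patient's record-based event follow-up to the common 12-month date, unless the patient withdraws permission for record access. Define where the 12 months start: Research Procedures places the last visit 12 months after the 16-week intervention, while Payment puts all three assessments within 12 months. Extend the record query explicitly to deaths, since it is now worded for rehospitalizations only.

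**SAP (Specific Aim 2).** Censor at the common date or at withdrawal of record permission. Run the same blinded record, database and hospital-form query for every patient. Report:

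1. An analysis using only record-ascertained events in all patients, so that detection does not depend on withdrawal status.
2. A sensitivity analysis censoring at dyad withdrawal, with exits tabulated by arm, by which member withdrew and by reason.

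**Cost.** Protocol, consent and SAP wording, plus record queries for withdrawn patients: 10-20% of 300, or about 30 to 60, under the assumed rates. The downside is that admissions outside the participating systems are captured less completely after exit.
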